8.3.4 Visit 5: Periodontal Surgery and Implantation of Investigational Device

Pre-surgical procedure:

- Collect blood serum sample for rh-bFGF antibody; and,

Periodontal surgery:

Beginning with the target tooth ranked as the most severe disease, the area selected for surgery is anesthetized. Following intracrevicular incisions, buccal and lingual full-thickness horizontal (mucoperiosteal) flaps are raised extending at least one tooth mesial and distal to the treated tooth. In case of a missing proximal tooth, the flap is extended at least 6 mm proximal to allow easier management and placement of the test material. Care is taken to preserve as much as possible of the keratinized gingival connective tissue in the flap. A horizontal releasing incision will be performed in order to facilitate coronal displacement of the flap, if it is applicable. The inner

surface of the flap may be carefully instrumented to remove dento-gingival epithelium and granulation tissue.

Following the reflection of the mucoperiosteal flap, all granulation tissue associated with the osseous defect is removed. Meticulous root planing should be performed to remove subgingival soft and hard deposits on the root surfaces. Magnification aids and fiber optic lights for additional illumination should be utilized. Additionally, both hand and ultrasonic instruments are to be used to assure thorough degranulation and root planing.

The area is rinsed with sterile saline. Examination of the defect and adjacent root surfaces should be performed to detect pathological conditions such as root fracture, severe root irregularities, cemental pearls or cervical enamel projections not easily removed by odontoplasty, root caries or subgingival and/or open restoration margins at the CEJ. These abnormalities must be successfully treated prior to proceeding or the subject will be excluded from the study.

Direct measurements of the intra-bony defect will be performed, as soon as the defect is thoroughly debrided, using a calibrated probe scoring the following dimensions:

- vBD (must be 4 mm or greater);
- W, the width of the defect from the root surface to the farthest bone wall; and
- The predominant number of bone walls present (i.e. 1-3)

At this point, final eligibility of the target tooth will be confirmed on the basis of the acceptable depth of the defect and the number of bone walls.

If the target tooth does not meet the inclusion criteria, the tooth will not receive the study treatment and standard care will be provided. If additional target teeth were identified during the screening process, the previous steps (up to determination of the final eligibility) will be performed on the next target tooth in order of ranking until a target tooth is deemed eligible or all have failed to meet the eligibility criteria. If all target teeth fail to meet the eligibility criteria, complete the Screening Failure Log and provide standard care.

If the target tooth meets the eligibility criteria, the steps below will be followed. Note that only one tooth per subject may receive treatment with the investigational product.

Decorticate cleaned defect with small round bar, and add neutral EDTA to condition the roots. The EDTA should be carefully applied to the tooth root surface with a small brush or other instrument avoiding excessive running of the paste onto the bone surfaces. After two minutes, the EDTA is removed using irrigation and suction.

Randomization

The subject is randomly assigned to a treatment group and the specified investigational device kit identified by the sequential product numbers on the label of the box is retrieved.

Implantation:

Following debridement of the periodontal defect, conditioning of the root surfaces with EDTA and measurements, the assistant opens the carton containing the investigational device (████████ GFeBGS) kit. All kits contain the β -TCP bone substitute. All kits will also have a vial with a lyophilized cake with or without rh-bFGF and a syringe containing a 1% HPC solution for reconstitution of lyophilized material. The vials are visually identical so the Investigators are unaware of the treatment assignment. The reconstituted solution in the vial should be left alone for a few minutes to release bubbles. Then the solution is mixed with the β -TCP bone matrix in the sterile container using a sterile instrument so that the graft particles are fully and rapidly saturated. The graft materials mixed with the solution should be implanted into the defect site within 5 minutes after mixing to avoid the nonspecific binding of rh-bFGF to the container. Please see Appendix E: Instructions for Use. During this time, the conditioned root surfaces are thoroughly rinsed and air-dried. The hydrated graft is then added into the osseous defect. The tissue flaps are coronally displaced and secured with interdental sutures (Gore-Tex[®] suture CV-5) in an attempt to achieve complete coverage of the surgical site.

Specific information related to the surgery, i.e. syringe number and approximate amount of product placed in the periodontal defect is then recorded on the Surgical Procedure form (CRF 4).

The subject should be instructed not to brush or floss the surgical site until the sutures are removed. Sutures will be removed at 2-3 weeks, when the clinician judges that the flap has become stabilized by healing. Subjects will be instructed to rinse with alcohol-free chlorhexidine (CHX) rinse (0.12%) twice daily for 2 weeks, and then once per day until the Visit 7 (4-wk post-operative visit). Note that subjects with dental work that predisposes them to staining will be instructed to swab CHX on the surgical site instead of rinsing with it.

Subjects will be treated with systemic application of antibiotics for post-surgery infection prophylaxis and will be instructed to take acetaminophen, if necessary, for pain relief after surgery. No NSAIDs or surgical dressing will be used.

If any adverse events occurred during the surgery, complete the Adverse Events form (CRF 8). If the subject was withdrawn from the study during the surgery, complete the Subject Discontinuation/Withdrawal form (CRF 10).

Photography:

Five clinical photographs of the target tooth should be taken at the following times:

- Before surgery;
- After flap reflection, debridement and root planing;
- With a probe in place vertically to the base of the defect;
- After the device is placed in the defect; and,
- After soft tissue closure

Post-surgical Care:

Analgesics prescribed will be recorded. All adverse events must be recorded.

8.3.5 Visits 6 and 7: Follow-up Evaluations

Subjects will be seen for post-operative evaluations at 2 and 4 weeks post-surgery (\pm 3 days). Sutures will be removed approximately 2 weeks post-surgery when the clinician judges that the flap has become stabilized by healing. Blood will be collected and prophylaxis for staining due to CHX rinsing or swabbing will be performed. Wound healing and the condition of the soft tissues in the surgical site will be examined by visual inspection and very gentle palpation. A secondary endpoint, WH score, will be recorded to reflect the extent of healing (WH) at the surgical site. Deep scaling of the target tooth should not be performed for the duration of the study and no additional implantation of the investigational product is allowed. Note that if a subject is diagnosed with a precancerous lesion such as leukoplakia after the study starts, it will be biopsied as appropriate for further analyses. A summary of all procedures to be performed is listed below:

Summary of Procedures/Measurements:

- Determine the WH score and evaluate the gingival wound
- Photographs of surgical site
- Supragingival cleansing by hand of surgical site
- Record date of suture removal and the number of days of work missed (if appropriate) on the Follow-up Evaluation form (CRF 5)
- Oral hygiene instruction and prophylaxis for staining due to CHX rinse or swab (as necessary)
- Concomitant medication review, especially number and type of analgesics
- Adverse Events review. Complete the Adverse Events form (CRF 8) if necessary
- Collect blood serum sample for rh-bFGF antibody

8.3.6 Visits 8 and 9: Subsequent Follow-up or Early Termination Evaluations

Subsequent follow-up visits occur at 3 and 6 months (final evaluation) post-surgery (\pm one week). During these visits, photographs are taken and the endpoint measurements of clinical attachment level (CAL), probing pocket depth (PD) and gingival recession (GR) will be assessed in the surgery site. Subjects with an increase of specific antibody production against rh-bFGF at Visit 7 will have blood serum collected until their results return to baseline values. Deep scaling of the target tooth should not be performed for the duration of the study and no additional implantation of the investigational product is allowed. Note that this visit is also conducted for early termination. Note that if a subject is diagnosed with a precancerous lesion such as leukoplakia after the study starts, it will be biopsied as appropriate for further analyses. A summary of all procedures to be performed is listed below:

Summary of Procedures/Measurements:

- Detailed probing measurements of the target tooth including:
 - CAL (calculation)
 - PD
 - GR
 - BOP
- Photographs of surgical site
- Routine supragingival prophylaxis
- Standardized PA radiograph of surgical site (see Section 8.1.3)
- Only at 3 months post-implantation: Oral hygiene instruction and full-mouth prophylaxis for staining due to CHX rinse or swab
- Record tobacco use on the Subsequent Follow-up Evaluation form (CRF 6)
- Concomitant medication review, especially number and type of analgesics since the last visit
- Complete the Subsequent Follow-up Evaluation form (CRF 6)
- Adverse Events review. Complete the Adverse Events form (CRF 8) if necessary
- If necessary, collect blood serum sample for rh-bFGF antibody

9.0 ADVERSE EVENTS

9.1 Definitions

9.1.1 Adverse Events

An adverse event (AE) is defined as any untoward medical occurrence in a subject; it does not necessarily have to have a causal relationship with the investigational device.

An AE can therefore be any unfavorable and unintended sign, symptom, or disease temporally associated with the use of the investigational device, whether or not it is considered related to the investigational device.

9.1.2 Additional Points to Consider for AEs

An untoward finding generally may:

- Indicate a new diagnosis or unexpected worsening of pre-existing condition of periodontitis. (Intermittent events for pre-existing conditions underlying disease should not be considered AEs.)
- Necessitate unexpected surgical intervention and/or medication.
- Be considered unfavorable by the Investigator for any reason.

Diagnoses vs. signs and symptoms:

- Each event should be recorded to represent a single diagnosis. Accompanying signs or symptoms should NOT be recorded as additional AEs. If a diagnosis is unknown, sign(s) or symptom(s) should be recorded appropriately as an AE(s).

Worsening or changes in severity of AEs:

- If the subject experiences a worsening or complication of an AE after any change, the worsening or complication should be recorded as a change to an existing AE.
- If the subject experiences changes in severity of an AE, the event should be captured once with the maximum severity recorded.

9.1.3 Expected AEs

Following the periodontal flap procedure, pain, swelling, soreness, erythema, edema, bleeding and temporary numbness are expected to occur 80% to 100% of the time. These sequelae are related to the surgical procedure, not the product and typically resolve over time as the wound heals. Occasionally (less than 5% of the time), fever, pus and infection of the surgical site may occur as post-surgical adverse events.

In addition, headaches, tooth pain and tooth disorder (less than 10%) were reported as AEs related to periodontal grafting procedures in the summary of effectiveness and safety data for a similar product (GEM 21S TM).

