3.5.3 Potential Risks Associated With rh-bFGF in GFeBGS

The rh-bFGF based product has been approved for treatment of dermal ulcers by the Japanese authority and in clinically used since 2001 with minimal adverse events reported in the post marketing surveillance report to the Pharmaceuticals and Medical Devices Agency for 8 years. Most of the adverse events were related to the skin and subcutaneous tissue and the administration site. There were rare reports of malignant tumors in the follow-up period whose causal relationship with the product could not be denied due to insufficient information. The safety and toxicological testing on rh-bFGF includes single dose toxicity, repeating dose toxicity, reproductive development toxicity, genetic toxicity (mutagenicity), local irritation, antigenicity, pyrogen test, skin carcinogenesis initiation, skin carcinogenesis promotion, effects on human tumor cells, effects on mouse melanoma cells, evaluation using a two-step model of hepatocarcinogenesis, *in vitro* transform study. No adverse events were observed throughout this series of studies. In summary, the safety, toxicity and biocompatibility data suggest that an rh-bFGF-based product is sufficiently safe for conducting a human clinical trial.

CONFIDENTIAL

However, the risk of promotion of cancer in a remote location cannot be denied because rh-bFGF has a promotional effect to accelerate a proliferation of various kinds of cells including several human tumor cell lines. Even though the probability of this risk is very low, its severity is considerable if it were to occur. To minimize the cancer promotion risk, the subjects with a history of oral cancer or having any other history of cancer (except for prostatic and skin cancer more than 5 years after treatment and skin cancer) are excluded in this study. If precancerous conditions of the mucous membrane are found in the oral cavity, it will be thoroughly examined and diagnosed before enrollment of the patient in this study. If the Investigator is unable to make a definitive diagnosis of the oral lesion, the Investigator will consult with an oral pathologist or a qualified specialist. Also, Investigators will be well trained about the proper preparation and use of GFeBGS before initiation of the study.

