9.1.7 Causality of AEs

The relationship of each AE to investigational device will be assessed using the following categories:

| RELATIONSHIP | DESCRIPTION |
|--------------|--|
| Not related | Any reaction that does not follow reasonable temporal sequence from administration of study device AND that is likely to have been produced by the subject's clinical state or other modes of therapy administered to the subject. |
| Unlikely | Any reaction that does not follow a reasonable temporal sequence from administration of study device or that is likely to have been produced by the subject's clinical state or other modes of therapy administered to the subject. |
| Likely | A reaction that follows a reasonable temporal sequence from administration of study device OR that follows a known response pattern to the suspected device AND that could not be reasonably explained by the known characteristics of the subject's clinical state or other modes of therapy administered to the subject. |
| Definite | A reaction that follows a reasonable temporal sequence from administration of study device AND that follows a known response pattern to the suspected device AND that recurs with rechallenge, and/or is improved by removing the device. |

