9.2.1.2 AE Reporting

At each study visit beginning with the Surgical Visit (Visit 5), the Investigator will assess whether any AEs have occurred. A neutral question, such as “How have you been feeling since your last visit?” may be asked. Subjects should be instructed to report AEs occurring at any other time during the study.

All subjects experiencing AEs, whether considered associated with the use of the investigational device or not, must be monitored until the symptoms subside and any clinically relevant changes in laboratory values have returned to baseline or until there is a satisfactory explanation for the changes observed. All AEs will be documented in the AE form, whether or not the Investigator concludes that the event is related to the investigational device. If the treatment involves surgical intervention, the Surgical Intervention form (CRF 7) must be completed. The following information will be documented for each adverse event:

- Event type
- Start and stop date
- Severity
- Investigator’s opinion of the causal relationship between the event and investigational device (Section 9.1.7)
- Investigator’s opinion of the causal relationship to study procedure(s), including the details of the suspected procedure
- Action concerning investigational device
- Outcome of event
- Severity (Section 9.1.6)

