12.1.11 Safety Analysis

All AEs will be coded according to the Medical Dictionary for Regulatory Activities (MedDRA) and additional pre-specified codes for device-specific local AEs or classified using a pre-specified ordinal scale. The classes of AEs will be summarized by type (by organ class and preferred term), incidence, timing (intra-operative, post-operative), severity, and relationship to study treatment for each treatment group; event counts will also be summarized by system organ class and preferred term. All AEs will also be sorted into local vs. systemic events. Patients reporting multiple

episodes will be counted once under the worst severity and the strongest relationship, respectively. In addition, SAEs will be presented by relationship to study treatment.

Local events, clinical signs or symptoms, rh-bFGF antibody above baseline, and delayed healing will also be assessed. The subject-level incidence of these outcomes will be analyzed using a two-sided Fisher Exact test while the event-level incidence will be analyzed using a Wilcoxon test.

Safety analyses will be performed on the ITT population receiving any study treatment.

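### Section 9.1.3 rules out a product cause for seven common local reactions, which contradicts the open, per-event device causality rating in 9.1.7 and 9.2.1.2

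*Protocol*

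**What the plan says.** Section 9.1.3 (Expected AEs) names seven reactions after the periodontal flap procedure: pain, swelling, soreness, erythema, edema, bleeding and temporary numbness. On frequency it says: "bleeding and temporary numbness are expected to occur 80% to 100% of the time". On cause it says: "These sequelae are related to the surgical procedure, not the product and typically resolve over time as the wound heals". The attribution carries no qualifier.

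The rating rules stand elsewhere. Section 9.1.7 begins: "The relationship of each AE to investigational device will be assessed using the following categories". It then defines four categories, from *Not related* to *Definite*. Section 9.2.1.2 requires every AE to be documented whether or not it is judged related. Among the items to record is the investigator's "opinion of the causal relationship between the event and investigational device", with a pointer to 9.1.7 and none to 9.1.3. A separate item is the investigator's "opinion of the causal relationship to study procedure(s), including the details of the suspected procedure". Section 8.1 blinds the investigator and all study personnel to treatment.

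Section 12.1.11 summarizes AEs by type, incidence, timing, severity and "relationship to study treatment for each" treatment group. A subject with several episodes is counted once, under the strongest relationship. The section also tests local events and clinical signs or symptoms between arms, with a Fisher exact test at subject level and a Wilcoxon test at event level.

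**The concern.** Calling an event expected after surgery is ordinary background. Section 9.1.3 goes further and excludes the product as a cause by type of event. Every arm has the same operation, so whether rh-bFGF adds to swelling or bleeding is one of the safety questions the trial can inform. The protocol should not answer it before any data exist.

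The tables by relationship in 12.1.11 are at stake. A rater who takes 9.1.3 at its word will give these events a lower device relationship than 9.1.7 alone would produce. The tables would then understate device-related local events for the reactions that most subjects will have.

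**Working it through.** The point is textual, so the check sets the sections side by side.

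**1. Is the attribution open or closed?** Section 9.1.3 is closed: procedure, not product, for seven named reactions. Sections 9.1.7 and 9.2.1.2 are open: each AE is rated for the device, and separately for the procedure. Two fields allow both causes to apply to one event. Section 9.1.3 treats them as alternatives.

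**2. Does the answer implied by 9.1.3 fit the scale?** *Not related* joins two conditions with AND: no reasonable temporal sequence from device administration, and a likely origin in the subject's clinical state or another therapy. Swelling at the graft site soon after implantation does follow a temporal sequence, so the first condition fails. *Unlikely* joins the same conditions with OR, so it is the lowest category such an event can reach. A rater who follows 9.1.3 to *Not related* therefore breaks 9.1.7.

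**3. Does the protocol's evidence establish the exclusion?** It points both ways.
- Section 3.5.3, on the marketed dermal rh-bFGF product, says: "Most of the adverse events were related to the skin and subcutaneous tissue and the administration site".
- Section 3.3 reports complications similar to placebo in two phase II studies of rh-bFGF gel in periodontal use. It also says that this trial is the first of the device in such subjects.

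Similar complications with a gel make a large effect less likely. They do not support a categorical exclusion for the combination with β-TCP.

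**4. How many subjects are concerned?** Inputs are 94 randomized (5.1) and 80% to 100% (9.1.3), taken as a share of subjects. 0.80 × 94 = 75.2 and 1.00 × 94 = 94, so about 75 to 94 subjects would have at least one rating of this kind. This counts the ratings exposed to the wording, not the misclassified ones.

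**5. How much can the unfiltered comparison show?** Assume the range applies to each reaction singly (the text could also mean any of them). Power of the exact two-sided Fisher test at 5%, by summing binomial outcomes:

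| Control vs dose | 20 per arm | 23 per arm |
|---|---|---|
| 80% vs 90% | 0.07 | 0.09 |
| 80% vs 95% | 0.17 | 0.22 |
| 80% vs 100% | 0.37 | 0.50 |
| 90% vs 100% | 0.04 | 0.07 |

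Simple incidence near its ceiling says little, so readers will lean more on severity and relationship. The limit comes from the base rate and arm size. Rewording 9.1.3 would not change it.

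**The case against.** The strongest reply is that 9.1.3 describes and does not instruct. It tells no one how to rate an event, sets no default and exempts nothing from recording. The operative rules in 9.1.7 and 9.2.1.2 still require a blinded device rating for every AE. This stands. A reader might infer that device causality is decided in advance for these events, or that the relationship table must show none in any arm. The text does not support that, because nothing in 9.1.3 overrides the rating. What remains is a contradiction that investigators must resolve for themselves, with a pull in one direction.

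A reader might also infer that a dose-related excess of local reactions would be hidden. That does not follow either.
- Section 12.1.11 compares local events between arms with no causality filter, and summarizes incidence and severity by arm.
- The wound-healing scale in 5.2.3 grades redness, edema and bleeding at two and four weeks without attribution.
- Under blinding, any pull should act about equally in all arms. It would dilute the relationship tables and would not favor one arm.
- Section 12.1.10 bases dose selection on the primary composite. The summary adds observed safety, but neither names the relationship tables.

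Finally, the documents do not establish that these reactions rise with dose. Section 3.5.3 gives indirect support, and section 3.3 points the other way.

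**Conclusion.** The contradiction is real and limited. Section 9.1.3 assigns cause by event type, while 9.1.7 and 9.2.1.2 require a judgement for each event, and the answer that 9.1.3 implies cannot meet the definition of *Not related*. The likely effect is a downward pull on device relationship in all arms, so that the 12.1.11 tables by relationship understate device-related local events. The size of the pull cannot be derived from the protocol. The conclusion assumes that some investigators let 9.1.3 inform their ratings and that blinding holds. The randomized comparison of local events, irrespective of attribution, is not affected.

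**What to change.** In 9.1.3, state that these reactions are expected after flap surgery and remove the words that exclude the product. Add that relationship to the device and relationship to the procedure are judged separately for each event under 9.1.7, with no default by event type. Section 12.1.11 needs no change, since it already compares local events regardless of assigned cause.

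The cost is one sentence replaced and a note in investigator training. No procedure, data field or analysis changes. The downside is that some local events may be listed as possibly device-related, which makes the relationship tables slightly less favorable.
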